4.3.1.2.2. EGPA Relapse

Endpoint

Proportion of participants with EGPA relapse

Specification

The frequency and percentage of participants with EGPA relapse for the observation period and for the follow-up period will be summarized. The frequency and percentage of participants with EGPA relapse will be categorized as 1 time, 2 times, and \geq 3times, and summarized. The frequency and percentage of EGPA relapse and the events that cause EGPA relapse (1-3 in the Step1 below) will also be summarized. A separate summary will be displayed for the events that cause EGPA relapse. A listing of EGPA relapse will also be produced.

Determination of EGPA relapse

EGPA relapse is defined as any of the following events with worsening EGPA*

- 1) Increased dose of OCS
- 2) Initiation/increased dose of immuno-suppressive agents**
- 3) EGPA treatment with hospitalization

* Worsening of EGPA: new onset of EGPA symptoms or worsening of existing clinical symptoms as assessed by 9 organ-systems.

** Immuno-suppressive agents: If the dose of immuno-suppressive agents increases for the same formulation or if the number of immuno-suppressive agents increases for EGPA treatment.

Event date is defined as:

- 1) Increased dose of OCS: **Date of increased dose**
- 2) Initiation/increased dose of immuno-suppressive agents: Date of initiation/Date of increased dose
- 3) EGPA treatment with hospitalization: Date of hospitalization

The first relapse occurred between two consecutive assessment time points will be counted as EGPA relapse for the first of the two assessment points. When assessment time points are scattered (i.e. Week 24 data is missing due to no clinic visit), events occurred within the last visit date + 84 days will be used as the determination for EGPA relapse.

Definition of Relapse Date

Set the starting point date for each of the following relapse conditions 1) to 3) and calculate the time to relapse (day).

The formula for calculating the time to relapse is relapse date – starting point date + 1

However, if the conditions 1) to 3) overlap, the shortest time (day) until relapse will be used.

1) Increase in OCS dose

- The date of relapse is the date of dose increase.
- The starting point date is the date of the end of dosing immediately before the dose increase or the earliest assessment date without symptoms of EGPA and dose reduction.

ex1) In the case of [dose reduction \rightarrow discontinuation \rightarrow dose increase], the starting point date is the end date of dosing (if the end date of dosing is missing, the start date of dosing) immediately before the most recent discontinuation before relapse date.

Assessment time points	Assessment date	EGPA symptoms	Start or end date of dosing	Condition of dosing	Dose (mg)
Nucala start date	2020/1/1	None		Ongoing since before Nucala dosing	10
			2020/1/2	End date of dosing	10
			2020/1/3	Start date of dosing	5
Week 12	2020/4/15			Ongoing dosing	5
			2020/4/16 (Starting point date)	End date of dosing	5
Week 24	2020/7/2	Active			None
			2020/7/3 (Relapse date)	Start date of dosing	10 (Increase)

ex2) In the case of [dose reduction \rightarrow dose increase], the starting point date is the start date of dose reduction immediately before relapse date.

Assessment time points	Assessment date	EGPA symptoms	Start or end date of dosing	Condition of dosing	Dose (mg)
Nucala start date	2020/1/1	None		Ongoing since before Nucala	10

				dosing	
			2020/1/2	End date of dosing	10
			2020/1/3 (Starting point date)	Start date of dosing	5
Week 12	2020/4/15	None		Ongoing dosing	5
				Ongoing dosing	5
Week 24	2020/7/2	Active	2020/7/2	End date of dosing	5
			2020/7/3	Start date of	10
			(Relapse date)	dosing	(Increase)

ex3) In the case of no dose reduction after Nucala dosing, the starting point date is the earliest assessment date without symptoms of EGPA.

Assessment time points	Assessment date	EGPA symptoms	Start or end date of dosing	Condition of dosing	Dose (mg)
Nucala start date	2020/1/1 (Starting point date)	None		Ongoing since before Nucala dosing	5
				Ongoing dosing	5
Week 12	2020/4/15	None		Ongoing dosing	5
			2020/4/16	End date of dosing	5
Week 24	2020/7/2	Active			None
			2020/7/3	Start date of	10
			(Relapse date)	dosing	(Increase)

2) Increasing the dose or initiation of immune-suppressive agents.

- Dose increases will be treated in the same way as for OCS.
- The date of relapse associated with new initiation is the start date of dosing.
- The starting point date is the earliest assessment date without symptoms of EGPA.

ex) The starting date is the earliest assessment date without symptoms of EGPA.

Assessment time points	Assessment date	EGPA symptoms	Start or end date of dosing	Condition of dosing	Dose (mg)
Nucala start date	2020/1/1	Active or worsening			None
					None
Week 12	2020/4/15 (Starting point date)	None			None

					None
Week 24	2020/7/2	Active or worsening			None
			2020/7/3	Start date of	10 (New
			(Relapse date)	dosing	initiation)

3) Treatment involving hospitalization

- The date of relapse is the date of hospitalization.
- The starting point date is the date of discharge immediately prior to relapse or the earliest assessment date without symptoms of EGPA.

ex1) If there is a discharge date immediately before the relapse, the starting point date is the discharge date immediately before the relapse.

Assessment time points	Assessment date	EGPA symptoms	Date of hospitalization or discharge	Condition of hospitalization or discharge
Nucala start date	2020/1/1	Active or worsening		Ongoing hospitalization
			2020/1/2 (Starting point date)	Date of discharge
Week 12	2020/4/15	None		
			2020/6/13 (Relapse date)	Date of hospitalization
Week 24	2020/7/2	Active or worsening		Ongoing hospitalization

ex2) If there is no discharge date immediately prior to relapse or if there is no discharge date exists (e.g. ongoing hospitalization, incomplete date), the starting point date is the earliest assessment date without symptoms of EGPA.

Assessment time points	Assessment date	EGPA symptoms	Date of hospitalization or discharge	Condition of hospitalization or discharge
Nucala start date	2020/1/1	Active or worsening		
Week 12	2020/4/15 (Starting point date)	None		
			2020/6/13 (Relapse date)	Date of hospitalization
Week 24	2020/7/2	Active or worsening		Ongoing hospitalization

Increased dose of OCS & Initiation/increased dose of immuno-suppressive agents

nmuno-suppr	ressive age	ents will be made as follows.			
	Conditi	on			
Increased dose	The day OCS: In equivale Immuno suppress number	The day after the visit date of Week 0 in this study: OCS: In case of the dose of OCS increased as prednisolone- equivalent Immuno-suppressive agents: In case of the dose of immune- suppressive agents increased for the same formulation or if the number of immune-suppressive agent increased			
Initiation	In case of number this does of admir	In case of an immune-suppressive agent is newly started (or the number of agents is added) after the start date of Nucala. However, this does not apply if the same agent is re-administered after the start of administration of the agent.			
Ν	ucala start d	ate at Week 0	Determination		
		100 mg	Initiation		
50 mg		100 mg	Initiation		
•	50 mg	100 mg	Increase		
•	50 mg	100 mg	Increase		
		50 mg 100 mg	• Initiation & Increase		
•	50 mg	100 mg	Increase		
		50 mg 100 mg	Increase		
		50 mg 100 mg	• Initiation & Increase		
	50 mg	25 mg 50 mg	Increase		
		50 mg 25 mg 50 mg	Initiation & Increase		
art date of]	End date of dosing				

The decision to increase the dose of OCS and to Initiation or increased dose of immuno-suppressive agents will be made as follows.

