#### 3.3.3. Withdrawal from Study

- A participant may withdraw from the study and stop reporting data at any time at his/her own or physician's request, or if they are lost to follow-up.
- To determine the safety and effectiveness of Nucala administration in participants who discontinued the treatment, a follow-up investigation (up to planned Week 96 of observation period) should be conducted wherever possible.
- If the participants enroll in another study involving investigational study treatment intervention while enrolled in this study, they will be withdrawn from the present study.

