# 4.6. Secondary and Exploratory Analyses

The secondary and exploratory analyses will be performed for the TP population. All endpoints will be summarised by using appropriate descriptive statistics.

The summary table will be also produced by the observation period and the follow-up period, respectively.

The endpoints selected for secondary and exploratory analyses are listed below by objective:

To investigate the long-term effectiveness of Nucala in adult patients with EGPA in Japan

- Proportion of participants with clinical symptoms as assessed by 9 organ-systems (i.e. systemic, skin, mucous membranes/eyes, ears/nose/throat, chest, cardiovascular, abdominal, renal, nervous system) for the observation period of 96 weeks.
- Proportion of participants with EGPA relapse for the observation period of 96 weeks.
   EGPA relapse is defined as any of the following with worsening EGPA.\*
  - 1) Increased dose of OCS.
  - 2) Initiation/increased dose of immuno-suppressive agents.\*\*
  - 3) EGPA treatment with hospitalization.
  - \* Worsening of EGPA: new onset of EGPA symptoms or worsening of existing symptoms.
  - \*\* Immunosuppressive agents: If the dose of immunosuppressive agents increases for the same formulation or if the number of immunosuppressive agents increases for EGPA treatment.
- Annualized rate (event/year) of hospitalization for EGPA-related events

213684

 Annualized rate (event/year) of emergency room/unscheduled visit for EGPA-related events

The annualized rate of hospitalization for EGPA treatment will be analysed by using a negative binomial generalized linear model with logarithm of time as an offset variable, from which the estimated event per year and associated 95% CIs will be calculated.

- Average daily dose (prednisolone-equivalent) of OCS over 96 weeks
- The proportion of subjects in the dosing categories\* relative to average daily OCS (prednisolone-equivalent) over 96 weeks
  - \* Zero, >0 to ≤4.0 mg/day, >4.0 to ≤7.5 mg/day, >7.5 mg/day

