4.3.1.2.3. Annualized Rate of Hospitalization for EGPA-related Events

Endpoint
Annualized rate (event/year) of hospitalization for EGPA-related events

Model Specification

The annualized rate of hospitalization for EGPA-related events will be analyzed by using a negative binomial generalized linear model with logarithm of time as an offset variable, without covariate. The annualized rate and associated 95% CIs will be calculated by exponential transform the value of intercept term and associated 95% CIs estimated when the above model was applied. The annualized rate will be calculated in observation period and retrospective period independently.

Terms in the model:

- **Response**: number of recorded, on-treatment, hospitalization for EGPA-related events experienced per participant.
- Offset: logarithm of treatment time in year

Observation period:

Treatment time in year for each participant will be calculated as:

Participants who complete the study:

 $\{(date of end of Nucala - date of start of Nucala) + 1\} / 365.25$

Participants who enter the follow-up period:

 $\{(date of end of Nucala + 28 - date of start of Nucala) + 1\} / 365.25$

For the raw value of calculation result, round off to two decimal places will be applied.

If the date of end of Nucala is missing, the date of start of the last administration of Nucala + 28 days will be imputed for the date of end of Nucala.

```
Retrospective period:
```

Treatment time in year for each participant will be calculated as:

48 / 52

```
SAS code:
```

```
proc genmod data = <dataset>;
  model n_hosp =
  / link=log dist=negbin offset=logfuinyears;
run;
data parm_est(keep= val rate rate_ll rate_ul);
  set out_parm(where=(parameter='Intercept'));
  format rate rate_ll rate_ul 8.2;
  val= "annualized rate of hospitalization for EGPA-related events
from negative binomial model without covariate";
  rate=exp(estimate);
  rate_ll=exp(lowerwaldcl);
  rate_ul=exp(upperwaldcl);
  run;
```

where n_hosp is the number of hospitalizations for EGPA-related events per participant in follow-up time, and logfuinyears is logarithm of the treatment time in years.

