4.8. Changes to Protocol Defined Analyses

There were no changes or deviations to the originally planned statistical analysis specified in the protocol amendment 01 (Dated: 27-JUL-2020).

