6.2.2. Study Period

Assessments and events will be classified according to the time of occurrence relative to the study period.

Screening period is defined as 0-4 weeks before the date of dose of Nucala at Week 0.

Observation period is defined as time from the date of dose of Nucala at Week 0 to the stop date of Nucala +28 days for the participants who did not withdraw from study, or the first treatment discontinuation date +28 days for the participants who withdraw from study. If the date of dose of Nucala at Week 0 is missing, the latest available date between the screening visit date and the Week 0 visit date will be used for the start date of the observation period. When the last Nucala stop date is missing, the last Nucala start date will be imputed.

Follow-up period is defined as time from the first treatment discontinuation date +29 days to 96 weeks within the observation period at maximum. The follow-up period is only applicable for the participants who discontinued the treatment.

Retrospective period is defined as time (within 12 weeks) before the first dose of Nucala. For data of hospitalization for EGPA-related events and ER/Unscheduled visit for EGPA-related events the period is defined as time (within 48 weeks) before the first dose of Nucala.

The study periods to use for summaries on each endpoint are as below.

A:	PMS period	B: Observation period
Retrospective		
period		

Participants who completed the study

Participants who discontinued and moved to the follow-up period

C:	PMS period	D: Observation	E: Follow-up
Retrospective		period	period
period			

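### Protocol-required EGPA hospitalization and ER-visit rates after stopping Nucala are missing from the SAP without being declared, and no relapse result covers Week 0 to Week 96 for all participants

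*SAP*

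**What the plan says.** **Protocol**
- Section 4.6 defines the relapse endpoint as "Proportion of participants with EGPA relapse for the observation period of 96 weeks". It also asks for secondary and exploratory tables by observation period and by follow-up period. Section 4.5, on adverse events, asks for a total period as well.
- Section 3.1 caps the observation period at 96 weeks and gives participants who stop Nucala a separate follow-up period. For them, Section 3.3.3 says "a follow-up investigation (up to planned Week 96 of observation period) should be conducted wherever possible".
- Appendix 1 marks EGPA hospitalization and ER/unscheduled visits for collection in follow-up.

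**SAP**
- Section 6.2.2 runs the observation period from the Week 0 dose "to the stop date of Nucala +28 days for the participants who did not withdraw from study", or to "the first treatment discontinuation date +28 days for the participants who withdraw from study". It continues: "Follow-up period is defined as time from the first treatment discontinuation date +29 days to 96 weeks within the observation period at maximum".
- Section 4.3.1.2.2 plans counts and percentages of "participants with EGPA relapse for the observation period and for the follow-up period will be summarized". Section 4.3.1.2 bases secondary analyses on the Treated Population (TP). No relapse denominator or censoring rule is stated, and Section 4.3.1.3 plans no sensitivity analysis.
- Section 4.3.1.2.3 takes on-treatment hospitalizations as the response and adds: "The annualized rate will be calculated in observation period and retrospective period independently". Section 4.3.1.2.4 does the same for ER/unscheduled visits.
- Section 4.8 says: "There were no changes or deviations to the originally planned statistical analysis".

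**The concern.** There are two separate issues.

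The first is a gap between protocol and SAP. For two secondary endpoints the protocol collects post-stopping data and asks for a follow-up table, but the visible SAP produces no rate from those data and says that nothing has changed. A reader of the study report would not learn how often participants were admitted or made unscheduled visits after stopping, nor that this had been planned.

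The second concerns how relapse can be read. A crude percentage over a period of unequal length treats a participant who stops relapse-free at Week 16 (about 20 weeks at risk including the 28 days) like one observed for 96 weeks. If participants doing badly are more likely to stop, time at risk is removed selectively. The observation-period figure then understates relapse to Week 96, and no planned result puts the two periods together.

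**Working it through.** **1. Passages side by side**

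| Endpoint | Protocol 4.6 tables | Collected in follow-up (Appendix 1) | Periods in the visible SAP |
|---|---|---|---|
| EGPA hospitalization rate | Observation, follow-up | Yes | Retrospective, observation |
| ER/unscheduled visit rate | Observation, follow-up | Yes | Retrospective, observation |
| EGPA relapse | Observation, follow-up | Hospitalization, medication and symptoms: yes | Observation, follow-up |

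The first two rows depart from the protocol. The third does not.

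**2. Inputs for size.** The documents give no relapse rate and no treatment-stopping rate. The nearest figures are the 10% dropout and about 120 participants in Protocol 3.5. That calculation reproduces: ln(0.20)/ln(0.985) = 106.5, so 107; 107/0.90 = 118.9, so 119, against about 120. It concerns adverse-event detection and serves here only as a source for N and the 10%. The rest is assumed: on-treatment 96-week relapse risk 20% to 40% (30% worked below); fraction stopping f from 10% to 30%; stop times uniform over 96 weeks; constant hazards; post-stopping hazard h = 1 to 3 times the on-treatment hazard.

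**3. Person-time left out of the two rates.** Total: 120 × 672/365.25 = 220.8 person-years. If stoppers stay in the study, each loses on average about 1.840/2 − 28/365.25 = 0.843 years. With 12 stoppers that is 10.1 person-years (4.6%); with 36 it is 30.4 (13.8%).

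**4. Observation-period relapse percentage (TP denominator).** Take 96 weeks as one time unit, so c = 28/672 = 0.0417 and λ = −ln(0.70) = 0.3567. The mean probability that a stopper relapses before the cut is

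A = (1 − c) − (e^(−λc) − e^(−λ))/λ + c(1 − e^(−λ)) = 0.9583 − 0.7998 + 0.0125 = 0.171.

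Reported percentage = (1 − f) × 0.30 + f × 0.171:
- f = 10%: 0.270 + 0.0171 = 28.7%
- f = 30%: 0.210 + 0.0513 = 26.1%

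**5. Relapse to Week 96 in everyone.** A stopper's mean risk is B = 0.300 for h = 1. For h > 1,

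B = 1 − [e^(−hλ)(e^((h−1)λ) − e^((h−1)λc))/((h−1)λ) + c·e^(−λ)].

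- h = 2: 1 − (0.5682 + 0.0292) = 0.4026
- h = 3: 1 − (0.4860 + 0.0292) = 0.4849 (from unrounded terms)

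Total = (1 − f) × 0.30 + f × B:
- f = 10%: 30.0%, 31.0% and 31.8% for h = 1, 2, 3. The gap to 28.7% is 1.3, 2.3 and 3.1 points. In 120 participants this is 34.5 relapsers against 36.0 to 38.2, or about 2 to 4 people.
- f = 30%: 30.0% (h = 1) to 35.5% (h = 3). The gap to 26.1% is 3.9 to 9.4 points.

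Over the whole grid the gap runs from 0.9 to 11.3 points, always an understatement.

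**The case against.** The strongest reply is that the split is the protocol's own design. Section 4.5 asks for a total period for adverse events, while Section 4.6 asks only for separate observation and follow-up tables for effectiveness. The relapse section of the SAP complies. An on-treatment summary also suits the effectiveness objective, and a result regardless of Nucala status mixes on-treatment, off-treatment and re-treated time. This stands, and it is why the relapse part is an improvement to the plan.

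Four stronger readings are tempting, and the documents do not support them:
- *The SAP shortened the protocol's 96-week period.* Protocol 3.1 makes 96 weeks a maximum and moves stoppers to a separate period. The 28 days can be read as specifying that boundary.
- *All early stoppers are counted as relapse-free.* Relapses before the cut still count. The TP denominator is itself inferred: the OCS section states it, the relapse section does not.
- *Relapses after stopping are lost.* They have a follow-up table, and SAP 4.3.1.2.2 plans a relapse listing. A relapse soon after the cut may also be credited to the preceding assessment point under 4.3.1.2.2, although 6.2.2 classifies by time of occurrence.
- *Post-stopping hospitalizations are not analysed at all.* They can enter as the third relapse component. What is missing is a rate.

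On size, the gap at 10% stopping is small beside sampling error: the 95% half-width at 30% and n = 120 is 1.96 × √(0.3 × 0.7/120), about 8 points. Protocol Section 5 already urges caution on effectiveness. That is fair, but the shortfall has a known direction and the data to remove most of it are collected.

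SAP 4.4 is redacted and some SAP text is not visible. Nothing is inferred from those gaps.

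**Conclusion.** The omission of follow-up-period rates for EGPA hospitalization and ER/unscheduled visits holds on the visible text. Protocol 4.6 asks for them, Appendix 1 collects the data, SAP 4.3.1.2.3 and 4.3.1.2.4 do not produce them, and 4.8 does not say so. This part needs no numerical assumption.

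The relapse part holds as a limitation of a protocol-conforming summary. If the denominator is the TP, participants who leave the observation period relapse-free are non-events with shortened time at risk, and there is no Week 0 to Week 96 estimate. The understatement is about 1 to 3 points at 30% risk and 10% stopping, and about 4 to 9 points at 30% stopping. These sizes rest on assumed rates, uniform stop times and constant hazards. They also take relapse to Week 96 as the target. For participants who leave the study, later relapses are unobserved and only censoring can address them.

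The time to relapse that the SAP derives does not fill the gap. It starts from a dose reduction, end of dosing, discharge or symptom-free assessment instead of Week 0, and no analysis of it appears in the visible text.

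**What to change.** 1. **SAP 4.3.1.2.3 and 4.3.1.2.4.** Add follow-up-period event counts, person-years and rates, with person-time running from first discontinuation + 29 days to study exit or Week 96. A total-period rate is optional. With few participants in follow-up, a crude rate with an interval may be all the data can support. If these summaries are not wanted, record the omission and the reason in 4.8.
2. **SAP 4.3.1.2.2.** State the relapse denominator for each period. Beside the existing on-treatment summary, add a Kaplan-Meier estimate of first relapse from Week 0 to Week 96 regardless of Nucala status, censored at study exit. If an on-treatment Kaplan-Meier estimate is also shown, note that censoring at stopping assumes stopping is unrelated to relapse risk.

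Cost: SAP wording and a few extra tables from data already collected. Follow-up numbers will be small, and the Week 96 relapse figure is likely to be slightly less favourable than the observation-period percentage.

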#### **Observation period**

During the observation period, which is scheduled for 96 weeks (approximately 2 years) at maximum, safety and effectiveness data are obtained at approximately 12-week intervals. The intervals may be shorter/longer or may be irregular depending on the usual pattern of healthcare visits.

Any data collected during the observation period are entered into eCRF. The assessments in the routine clinical practice during the observation period are shown in Section 9.1 (Appendix 1).

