4.6.4. Subgroup analyses

The following subgroups are of interest in this study. A separate exploratory analysis of the prespecified endpoints within each subgroup will be carried out. Subgroup categories may be further collapsed if there are a small number of participants within a subgroup.

The following subgroups are of interest:

- Period from EGPA diagnosis to Nucala administration (year) (≤ 1, 1 < ≤ 2, 2 < ≤ 5, 5 < ≤ 10, 10 <)
- Severity of EGPA disease (1-2, 3, 4-5)
- Average daily dose (prednisolone-equivalent) of oral corticosteroid (OCS) over the observation period (0 mg/day, 0 < ≤ 4 mg/day, 4 < ≤ 7.5 mg/day, 7.5 mg/day <)
- ANCA (Positive, Negative)
- Immuno-suppressive therapy (Yes, No)

• EGPA disease relapse (Yes, No)

The following will be presented for each subgroup, based on the TP:

- summary of all AEs by the observation period and by the total period (the observation period and the follow-up period)
- frequency of participants with clinical symptom assessed by 9 organ-systems at each assessment visit by the observation period
- frequency of participants with EGPA relapse by the observation period
- summary of average daily dose of OCS at each assessment visit by the observation period
- plot of participants with clinical symptom assessed by 9 organ-systems at each assessment visit by the observation period
- box plot of median of average daily dose of OCS at each assessment visit by the observation period

• line plot of median of average daily dose of OCS at each assessment visit by the observation period In addition, the demographic and baseline characteristics will be summarized for the following subgroups.

- Completion/Discontinuation of the study
- With/Without clinical symptoms as assessed by 9 organ-systems at Week 48 and Week 96

Subgroup	EP1	EP2	EP3	EP4
Period from EGPA diagnosis to Nucala administration	Y	Y	Y	Y
Severity of EGPA disease	Y	Y	Y	Y
Average daily dose (prednisolone-equivalent) of oral corticosteroid (OCS) over the observation period	Y	Y	-	Y
ANCA	Y	Y	Y	Y
Immuno-suppressive therapy	Y	Y	Y	Y
EGPA disease relapse	Y	-	Y	Y

EP1: Proportion of participants with each of the clinical symptoms as assessed by 9 organ-systems EP2: Proportion of participants with EGPA relapse

EP3: Average daily dose (prednisolone-equivalent) of oral corticosteroid (OCS) over the observation period

EP4: Frequency of Adverse events (AEs)

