6.2.4. Assessment Window

The assessment time points defined below are used in the analysis. When calculating the assessment date, the visit closest to the specified date is used, and if the period from the specified date is the same, the latest visit is used.

Assessment window will be applied to early withdrawal dates. If participants prematurely withdraw from the study and do not have the visit date of Week 96, 673 days after Week 0 will be imputed to missing visit date of Week 96.

If the derived data based on the study day is included in the range of period, the corresponding week is assigned as below and will be used for analysis.

Assessment time points	Specified data	Window	Period	iod (day)	
Assessment time points	specified date	(±day)	From	to	
Week 0	1	-	-28	1	
Week 12	85	28	57	113	
Week 24	169	28	141	197	
Week 36	253	28	225	281	
Week 48	337	28	309	365	
Week 60	421	28	393	449	
Week 72	505	28	477	533	
Week 84	589	28	561	617	
Week 96	673	28	645	701	

The following shows the assessment window for the follow-up period.

Assessment time noint	Specified data	Window	Period (day)	
Assessment time point	specified date	(±day)	From	to
Follow Week 0	1	-	-	1
Follow Week 12	85	28	57	113
Follow Week 24	169	28	141	197
Follow Week 36	253	28	225	281

Assessment time point	Specified date	Window	Period (day)	
		(±day)	From	to
Follow Week 48	337	28	309	365
Follow Week 60	421	28	393	449
Follow Week 72	505	28	477	533
Follow Week 84	589	28	561	617
Follow Week 96	673	28	645	701

OCS dose and immuno-suppressive therapy is recorded on a daily basis and will be averaged into 12-weekly periods as below. If the date of dose of Nucala at Week 0 is missing, the latest available date between the screening visit date and the Week 0 visit date will be used for the start date of the observation period.

12-weekly period	First date	Last date
Weeks 9-12	Nucala start date at Week 0 +	Nucala start date at Week 0 +
	56 days	84 days
Weeks 21-24	Nucala start date at Week 0 +	Nucala start date at Week 0 +
	140 days	168 days
Weeks 33-36	Nucala start date at Week 0 +	Nucala start date at Week 0 +
	224 days	252 days
Weeks 45-48	Nucala start date at Week 0 +	Nucala start date at Week 0 +
	308 days	336 days
Weeks 57-60	Nucala start date at Week 0 +	Nucala start date at Week 0 +
	392 days	420 days
Weeks 69-72	Nucala start date at Week 0 +	Nucala start date at Week 0 +
	476 days	504 days
Weeks 81-84	start date at Week $0 + 560$	Nucala start date at Week 0 +
	days	588 days

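### After a missed visit, the SAP's 84-day limit leaves later dated relapse events uncounted while the participant stays in the denominator as relapse-free

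*SAP*

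**What the plan says.** The protocol (section 4.6) sets the secondary endpoint as "Proportion of participants with EGPA relapse for the observation period of 96 weeks". In its description of the observation period it expects uneven attendance: "The intervals may be shorter/longer or may be irregular depending on the usual pattern of healthcare visits".

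SAP 4.3.1.2.2 defines relapse as one of three dated events (increased OCS dose, start or increase of an immunosuppressant, EGPA treatment with hospitalization) accompanied by worsening EGPA. It then gives two counting rules. Between two consecutive assessment points, the first relapse counts wherever in the interval it falls. If a time point is missing because there was no visit, "events occurred within the last visit date + 84 days will be used as the determination for EGPA relapse".

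Nothing in the SAP says what happens to a dated event after that limit and before the next attended visit. Nothing treats the rest of the gap as unassessed. SAP 4.3.1.2 bases the secondary analyses on the Treated Population and gives no separate denominator for relapse. SAP 4.8 states that the analysis does not depart from protocol amendment 01.

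**The concern.** The limit discards information that the study holds. Each event type has its own date in SAP 4.3.1.2.2, and SAP 6.2.4 says: "OCS dose and immuno-suppressive therapy is recorded on a daily basis and will be averaged into 12-weekly periods as below". An event late in a gap can be placed on the calendar, yet the rule does not use it, and the participant is reported as relapse-free if no other event qualifies.

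This is a single-arm study, so no comparator offsets the loss, and the error has one direction: an uncounted relapse can only lower the proportion. It also carries into the counts of one, two, and three or more relapses, and into SAP 4.6.4, where relapse (yes or no) is a subgroup factor for adverse events, symptoms and OCS dose. A participant whose only relapse lies in an excluded stretch is placed in the no-relapse group.

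**Working it through.** The plan gives no figure for relapse, so there is none to reproduce. The inputs are the 84-day limit (SAP 4.3.1.2.2), the visit windows of ±28 days (SAP 6.2.4: Week 12 is Days 57–113, Week 24 Days 141–197, Week 36 Days 225–281), an observation period of 96 × 7 = 672 days, and about 120 participants (SAP 5).

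**1. Days excluded.** Excluded days = next attended visit − (last visit + 84).

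- One missed visit, nominal dates (Week 12 on Day 85, Week 36 on Day 253): the gap is 253 − 85 = 168 days and counting stops at Day 169. Excluded: 253 − 169 = 84 days, which is 50% of the gap and 84/672 = 12.5% of the period.
- Two consecutive missed visits (Day 85 to Day 337): the gap is 252 days. Excluded: 252 − 84 = 168 days, and 168/672 = 25%.
- One missed visit, all attended visits inside their windows: shortest gap 225 − 113 = 112, excluded 28; longest gap 281 − 57 = 224, excluded 140.
- With a visit outside the windows, the stretch shrinks. A visit on Day 198 carries the limit to Day 282, past the whole Week 36 window, so nothing is excluded. A visit on Days 114–140 leaves 1 day (225 − 224) to 83 days (281 − 198).

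**2. Comparison with attended visits.** Consecutive attended visits may lie 197 − 57 = 140 days apart, and every event between them counts. An event 139 days after a visit can therefore count in that case, but one 85 days after a visit cannot count once a visit is missed. In the SAP's own examples, the first assessment (2020/1/1) and Week 12 (2020/4/15) are 105 days apart, already beyond 84.

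**3. Which visit shows the worsening.** In the OCS examples and the immunosuppressant example, the event falls the day after a symptomatic visit (visit 2020/7/2, event 2020/7/3). In both hospitalization examples, Week 12 (2020/4/15) shows no symptoms, admission is on 2020/6/13, and Week 24 (2020/7/2) shows active or worsening disease. Both are labelled relapse, so the SAP accepts worsening seen at the later visit. Had Week 24 been missed, an admission on 2020/7/9 (85 days after Week 12) would not count, whatever Week 36 showed.

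**4. Effect on the proportion (assumptions).** The documents give neither the relapse rate nor the number of missed visits. Assume a constant relapse rate, a true 96-week proportion p of 10% to 40%, and a share m of participants affected of 10% to 50%. For u excluded days, the counted proportion in an affected participant is p′ = 1 − (1 − p)^(1 − u/672), and the overall loss is m × (p − p′).

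| p | p − p′, u = 84 | p − p′, u = 168 |
|---|---|---|
| 10% | 1.19 points | 2.40 points |
| 20% | 2.26 points | 4.59 points |
| 40% | 3.96 points | 8.17 points |

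- One missed visit each: from 0.10 × 1.19 = 0.12 points (0.14 of 120 participants) to 0.50 × 3.96 = 1.98 points (2.37 of 120).
- Two consecutive missed visits each: from 0.10 × 2.40 = 0.24 points (0.29 of 120) to 0.50 × 8.17 = 4.09 points (4.90 of 120).

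The loss would be larger if visits tend to be missed around relapses.

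**The case against.** The strongest defence is that relapse needs worsening as well as a dated event, and symptoms are assessed only at visits. The 84 days would then limit how long one visit's symptom status is carried forward: one nominal 12-week interval. The OCS and immunosuppressant examples fit this. The SAP does not state that purpose, however, and the hospitalization examples do not fit it. If the rest of the gap cannot be assessed, it should be handled as unassessed, not counted as relapse-free. What stands is that the size of the loss depends on which visit must show worsening, and the SAP does not say.

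A second defence is that the sentence only assigns a relapse to an assessment point and does not restrict the total for the period. That is possible, but no rule assigns or counts the later events, so the text needs correcting on this reading too.

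Third, the study is descriptive, the protocol (section 5) already warns that effectiveness data will be limited, OCS dose and hospitalization are reported separately, and the profile plots in SAP 4.6.1 keep such events visible. This limits the harm but does not correct the endpoint.

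A reader might also infer a plain contradiction with SAP 4.3.1.2.3, which models the "number of recorded, on-treatment, hospitalization for EGPA-related events experienced per participant" with no 84-day limit. That goes too far: the hospitalization endpoint does not require worsening and relapse does, so the two may differ by definition.

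**Conclusion.** The point holds as a fault in the stated counting rule. As worded, it covers less than the protocol's 96-week endpoint, the difference is not declared in SAP 4.8, and any error is downward. The excluded time is 12.5% of the period for one missed visit and 25% for two in a row, at nominal dates with no visit between windows. The effect on the proportion is probably small, about 0.1 to 2 points for one missed visit each, but that range rests wholly on assumed relapse and missed-visit rates and a constant hazard. A participant is lost only if every relapse he or she has falls in an excluded stretch. The Treated Population denominator comes from the general rule for secondary analyses.

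Three stronger readings are not supported:

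- That the reported proportion will be materially wrong. The documents give no rates from which to show this.
- That at least 28 days are always lost after a missed visit. This fails when a visit takes place outside the windows.
- That the OCS criterion itself is defective because no dose comparator is stated for a first start, or for a restart at or below the previous dose. That is at most missing detail. It sits beside a determination figure that cannot be read in the available text, so no conclusion is drawn.

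**What to change.** Change the SAP only; the protocol sets no rule for missed visits and needs no amendment.

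1. State which visit (before the event, after it, or either) must show worsening.
2. Report the proportion with relapse counting dated events up to the next attended visit when a qualifying visit shows worsening, beside the proportion under the 84-day rule.
3. Report how many participants have dated events in gaps that the 84-day rule leaves uncounted.
4. Record the difference from the protocol endpoint in SAP 4.8.

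The cost is one derivation reprogrammed on data already collected, plus wording. The downside is possible upward misclassification: counting to the next attended visit can link symptoms and events across a gap of up to 224 days after one missed visit. Showing both versions lets the reader see the range, and keeping the 84-day result preserves comparability with the interim report.
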